9. SAFETY EVALUATION

Subjects in safety analyses will be analyzed according to randomization assignment, using the safety analysis population.

9.1. Demographic and Other Baseline Characteristics

Summaries of age, gender, enrollment site, ethnicity, race, initial antibiotic therapy, initial treatment locations, and age group (<24 months vs. 24-71 months) will be presented by site (Table 9 and Table 10) or by treatment group and overall (Table 11 and Table 12). Ethnicity will be categorized as Hispanic or Latino, or not Hispanic and not Latino. In accordance with NIH reporting policy, a subject's guardians may designate the subject as belonging to more than one race or may refuse to identify a race, the latter reflected in the CRF as "No" to each racial option.

Summaries of subject's medical history will be presented by MedDRA® system organ class (SOC) and treatment group (Table 13).

Individual subject listings for all demographics (Listing 5) and pre-existing medical conditions (Listing 6) will be presented.

9.1.1. Concurrent Illnesses and Medical Conditions

Physical assessment findings from the enrollment visit, and any follow up visits, will be included in Listing 11.

9.1.2. Prior and Concurrent Medications

All concomitant medications taken within 30 days of signing the informed consent or during the study period will be recorded. Concomitant medications will be coded to the Anatomical Therapeutic Classification using the WHO Drug Dictionary. A by-subject listing of concomitant medication use will be presented (Listing 12). The use of concomitant medications during the study will be summarized by ATC1, ATC2 code and treatment group (Table 56).

9.2. Measurements of Treatment Compliance

Treatment was administered to subjects at their homes by a parent or caregiver. The number of subjects receiving the first dose of study product will be tabulated by site, treatment group, and time period (Table 6). The number of doses of study product administered will be presented by treatment group (Table 7, Listing 7).

9.3. Adverse Events

When calculating the incidence of AEs over multiple days (i.e., on a per subject basis), each subject will only be counted once and any repetitions of AEs within a subject will be ignored; the denominator will be the total population size on the first day of the time period (Day 1). For tabulation of AEs by day, the denominator will be the number of subjects enrolled and not withdrawn from the study by the day being described. All AEs reported will be included in the summaries and analyses.

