7.4 Final Study Visit

Visit 3: Outcome Assessment Visit #2, Day 19-25

Subjects will be seen for a follow-up visit on Day 19-25. Prior to this visit, study staff will make a preliminary assessment of the clinical response using the electronic health record to determine whether any of the following events have occurred since the previous visit.

- The subject had a medically attended visit to an ED, urgent care, or clinic;
- The subject was hospitalized;
- The subject received non-study, systemic antibiotic therapy;
- The subject underwent drainage of pleural fluid, placement of a chest tube, or video assisted thoroscopic surgery.

At the follow-up visit, study staff will complete the following procedures:

- Medical history to determine whether medically attended visits, receipt of non-study systemic antibiotics, or surgical procedures have occurred;
- Assessment of adequate clinical improvement as indicated by a parental report of lack of rectal, tympanic, axillary, or oral temperature $\geq 38.3^{\circ}\text{C}$ or 100.9°F for >24 hours, normalization of respiratory rate for age (<50 breaths/minute for children <24 months of age and <40 breaths/minute for children 24-71 months of age), and grading of cough.
- Physical assessment to determine vital signs (temperature, pulse, and respiratory rate) and physical assessment (general appearance, hydration status, work of breathing, presence of skin rash);
- Review of the subject's memory aid to assess and record any solicited events and concomitant medications;
- Review of potential protocol-defined SAEs
- Review of memory aid assess treatment compliance (if not reviewed at Visit 2);
- Collection of study product bottle for drug accountability, if not collected at Visit 2 and if available
- Collection of a throat swab and stool specimen (if available), if consented for future use samples.

If the subject develops signs or symptoms of pneumonia (including fever, increased work of breathing, or increased cough) or develops a severe solicited event, the child will be referred to his/her primary care provider or local urgent care center/ED. Study staff will assist in facilitating the follow up appointment. The study staff will share all pertinent information related to the study with the primary physician.

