An assessment of clinical response will occur at each follow-up visit. The assessment will include parental documentation of maximum temperature in the preceding 24 hours; normalization of respiratory rate; presence and extent of cough; occurrence of medically attended visits including visits to the ED, primary care physician, and urgent care; hospitalizations; use of non-study systemic antibiotics (parenteral or oral); and occurrence of surgical procedures. Vital signs (temperature, pulse and respiratory rates) will be collected at the enrollment visit and at each follow-up visit.

Solicited event assessments will include an assessment of solicited events occurring from the time of enrollment through the last visit, Visit 3. All subjects will complete a subject memory aid from the time of enrollment through Visit 3. Subject memory aids will be reviewed with the subject's parents for any discrepancies or missing data and will be returned to the subject's parent(s).

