9.3.1. Solicited Events

Solicited events will be captured daily until Outcome Assessment Visit #1; thereafter, parents/legal guardians will report symptoms based on memory aid and medical interview by study staff. For those with multiple solicited events, the ordinal response table will be based upon the most severe solicited event.

Solicited events were recorded for trial Days 1-25, or until study completion or termination, as the maximum severity for each day. Target solicited events include irritability, vomiting, diarrhea, allergic reaction, stomatitis, and candidiasis.

The proportion of subjects in each treatment group experiencing each solicited event with mild or greater severity will be tabulated by day and overall (Table 49 and Table 50). The proportion of subjects in each treatment group experiencing each solicited event will also be tabulated by day and severity level (Table 51 and Table 52). Finally, solicited events will be analyzed by taking the most severe response over the follow-up period, dichotomizing into a binary variable (none or mild versus moderate or severe) (Table 53). Proportions for these derived binary variables will be reported along with 95% exact confidence intervals. Comparisons of proportions by treatment groups will be given as odds ratios (with 95% exact confidence intervals) and p-values from Fisher's Exact Tests.

The maximum severity occurrence of each solicited event and cough (proportion of subjects for each severity level) will be plotted for each solicited adverse event (Figure 24). Solicited events by subject will also be presented (Listing 8).

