14.3 Safety Data

14.3.1 Displays of Adverse Events

14.3.1.1 Solicited Adverse Events

Table 49: Number and Percentage of Subjects Experiencing Solicited Events with 95% Confidence Intervals by Symptom, Dose, and Treatment Group - Standard Course

Standard Course																														
Symptom	Day 1 (N=X)			Day 2 (N=X)			Day 3 (N=X)			Day 4 (N=X)			Day 5 (N=X)			Day 6-9 (N=X)			Day 10-13 (N=X)			Day 14-18 (N=X)			Day 19-25 (N=X)			Day 1-25 (N=X)		
	n	%	95% CI	n	%	95% CI	n	%	95% CI	n	%	95% CI	n	%	95% CI															
Any Symptom	x	xx	x.x, x.x	x	xx	x.x, x.x	x	xx	x.x, x.x	x	xx	x.x, x.x	x	xx	x.x, x.x															
Irritability																														
Vomiting																														
Diarrhea																														
Allergic Reaction																														
Stomatitis																														
Candidiasis																														

N = Number of subjects in the Safety Analysis Population in the respective treatment group and with severity grades collected for each solicited symptom on the respective day or days.

Table with similar format:

Table 50: Number and Percentage of Subjects Experiencing Solicited Events with 95% Confidence Intervals by Symptom, Dose, and Treatment Group – Short Course

Table 51: Number and Percentage of Subjects Experiencing Solicited Events by Symptom, Maximum Severity, Dose, and Treatment Group – Standard Course

Symptom	Severity	Standard Course								
		Day 1 (N=X) n (%)	Day 2 (N=X) n (%)	Day 3 (N=X) n (%)	Day 4 (N=X) n (%)	Day 5 (N=X) n (%)	Days 6-9 (N=X) n (%)	Days 10-13 (N=X) n (%)	Days 14-18 (N=X) n (%)	Days 19-25 (N=X) n (%)
Irritability	None	x (x)	x (x)	x (x)	x (x)					
	Mild	x (x)	x (x)	x (x)	x (x)					
	Moderate	x (x)	x (x)	x (x)	x (x)					
	Severe	x (x)	x (x)	x (x)	x (x)					
Vomiting	None	x (x)	x (x)	x (x)	x (x)					
	Mild	x (x)	x (x)	x (x)	x (x)					
	Moderate	x (x)	x (x)	x (x)	x (x)					
	Severe	x (x)	x (x)	x (x)	x (x)					
Diarrhea	None	x (x)	x (x)	x (x)	x (x)					
	Mild	x (x)	x (x)	x (x)	x (x)					
	Moderate	x (x)	x (x)	x (x)	x (x)					
	Severe	x (x)	x (x)	x (x)	x (x)					
Allergic Reaction	None	x (x)	x (x)	x (x)	x (x)					
	Mild	x (x)	x (x)	x (x)	x (x)					
	Moderate	x (x)	x (x)	x (x)	x (x)					
	Severe	x (x)	x (x)	x (x)	x (x)					
Stomatitis	None	x (x)	x (x)	x (x)	x (x)					
	Mild	x (x)	x (x)	x (x)	x (x)					
	Moderate	x (x)	x (x)	x (x)	x (x)					
	Severe	x (x)	x (x)	x (x)	x (x)					

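### SAP 9.3 and the notes to Tables 49-52 give different solicited-event denominators, and Table 53 is left with the rule that counts missing diaries as event-free

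*SAP*

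**What the plan says.** The SAP gives three rules that could set the denominator of a solicited-event percentage.

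- **SAP 9.3, Adverse Events.** For tabulation by day, "the denominator will be the number of subjects enrolled and not withdrawn from the study by the day being described". For incidence over several days, "the denominator will be the total population size on the first day of the time period (Day 1", with the closing bracket following.
- **SAP Appendix 1, notes to Tables 49, 51 and 52** (Table 50 follows the Table 49 format). N is the safety-population children in the arm "with severity grades collected for each solicited symptom on the respective day or days".
- **SAP 6.1, General Principles.** Percentages rest on the non-missing sample size, while the N printed on a table includes missing observations.

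Table 53 covers the whole follow-up, with odds ratios, exact confidence intervals and Fisher p-values. It shows only N=X and has no note.

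On what is observed, Protocol 8.1 says: "All subjects will complete a subject memory aid from the time of enrollment through Visit 3". Protocol 7.4 sets that visit: "Subjects will be seen for a follow-up visit on Day 19-25". SAP 9.3.1 agrees: "Solicited events were recorded for trial Days 1-25, or until study completion or termination, as the maximum severity for each day".

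**The concern.** A solicited event can be counted only where a grade was recorded. If the denominator also includes children with no recorded grade, they enter the percentage as children without the event. SAP 9.3 does this and the table notes do not. A programmer following the text and one following the shells would therefore produce different percentages for the same cells.

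This matters most for Table 53, the only one of these five tables with a between-arm test, because no note there overrides 9.3. The protocol collects no unsolicited adverse events, so the solicited-event tables carry much of the tolerability evidence.

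**Working it through.** The plan states no numerical result for this rule, so there is no figure to reproduce. The check is a comparison of texts followed by a short count.

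**Step 1: what 9.3 governs.** SAP 9.3.2 rules out unsolicited events, and SAP 9.4 gives SAEs as listings and narratives. The by-day rule in 9.3 can therefore only be meant for solicited events, which are its own subsection 9.3.1. It is not a general sentence aimed at other data.

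**Step 2: the rules side by side.**

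| Output | SAP 9.3 | Table note | SAP 6.1 |
|---|---|---|---|
| Tables 49-52, single days (Days 1-5) | not withdrawn by that day | grades collected that day | non-missing |
| Tables 49-52, pooled columns (Days 6-9, 10-13, 14-18, 19-25; also 1-25 in Tables 49-50) | Day 1 population | grades collected on the day or days | non-missing |
| Table 53, whole follow-up | Day 1 population | none | non-missing |

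No sentence ranks these. For Table 53 the specific rule in 9.3 would normally override the general one in 6.1. The printed N does not settle the matter, because 6.1 has it include missing observations.

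**Step 3: effect of missing diaries under 9.3.** Let p be the event proportion among children with a grade, and m the share of the denominator with no grade.

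- Reported proportion under 9.3 = p × (1 − m). Under the table notes it is p.
- Proportional understatement = m.
- Reported risk ratio between arms = true ratio × (1 − m_short)/(1 − m_standard). It is undistorted only if m is equal in the two arms.

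The documents give no value for m, so no percentage is attached.

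**Step 4: one day or every day in a pooled column.** Table 42 (cough) requires at least one severity grade on the day or days. The notes to Tables 49-52 omit those words. Take the Day 19-25 column with about 200 children per arm (Protocol 5.3.1), every Visit 3 in window, diaries filled in through the visit day, and no withdrawals. A child seen on Day d contributes d − 18 days, which runs from 1 (Day 19) to 7 (Day 25).

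- At least one graded day: every child qualifies, 200 of 200.
- Every day graded: only children seen on Day 25 qualify, so the share is P(Visit 3 on Day 25).

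The distribution of visit days is not given. Under assumed distributions:

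| Visit 3 days over Days 19-25 | Share with all 7 days | Children of 200 |
|---|---|---|
| Uniform | 1/7 = 14.3% | 29 |
| Centred on Day 22 (5/10/20/30/20/10/5%) | 5% | 10 |
| Early (40/25/15/10/5/3/2%) | 2% | 4 |
| All on Day 25 | 100% | 200 |
| All on Day 19 | 0% | 0 |

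Under uniform visit days, N for one column is 29 or 200 depending on how the note is read. The Day 1-25 column in Tables 49-50 has the same ambiguity.

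**The case against.** The strongest reply is that the tables already carry the better rule. SAP 9.3.1 sends the by-day proportions to Tables 49-52, and their notes restrict N to children with grades collected. That is right for those four tables and makes the conflict there a matter of alignment. It does not cover Table 53, and 9.3 still stands as a stated rule.

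Three stronger readings are tempting, and the documents support none of them.

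- A reader might infer that daily rates late in the Visit 3 window will be understated because children who have completed are not withdrawn. No table reports those days singly: the shells show single days for Days 1-5 and pool the rest. In the pooled Day 19-25 column, every child with an in-window visit and a completed diary has at least one reportable day. What remains is unequal observation time.
- A reader might infer that never-dosed children are counted. SAP 9 applies the safety population, which SAP 6.3.4 limits to children who received study product.
- A reader might take the ~10% sample-size allowance as a further understatement. That allowance is for loss to follow-up, which Protocol 5.3.3 and SAP 4.3.3 list as a reason for withdrawal, so such children leave the by-day denominator. The Day 1 rule would keep them, but they may have diary data from before they left, and the allowance does not estimate blank diaries.

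It is also fair to say that a Day 1 population is a conventional base for per-subject incidence, and that an at-least-one-grade rule treats a one-day diary as observed follow-up. Both points stand. The second is why observed diary days should be shown. Finally, visit windows are the same in both blinded arms, so no between-arm bias has been demonstrated.

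**Conclusion.** The point holds as an unresolved inconsistency of minor severity. SAP 9.3 contradicts the notes to Tables 49-52 and the non-missing rule in SAP 6.1. It counts children without diary data as event-free, and it is the only adverse-event denominator left for Table 53. The resulting understatement equals the share of children with no grade, which the documents do not give. Separately, the pooled-column wording leaves N for Days 19-25 open between all diary-keepers and about 14% of them; the 14% rests on assumed uniform visit days and ranges from 0% to 100% over the extremes.

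The effect stops at the safety tables. DOOR uses solicited events from Days 1-5 at the first outcome visit and Days 1-18 at the second (SAP 3.3). The secondary solicited-event comparisons in Tables 18-23 use the complete-case cohorts, define their own N and end at Day 18.

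**What to change.** Replace the two denominator sentences in SAP 9.3 with: *safety-population children with at least one severity grade recorded for that event on that day or in that period*. Use the same wording in the notes to Tables 49-52, which settles the pooled columns in line with Table 42, and add it as a note to Table 53. For the Day 19-25 column, also report the number of diary days observed in each arm, because each child contributes between 1 and 7 days there.

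The cost is two sentences in the SAP and revised table notes. No new data are needed. Denominators will vary slightly by event and by day. The rule does not repair incomplete follow-up, but it makes it visible.

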9.3.1. Solicited Events

Solicited events will be captured daily until Outcome Assessment Visit #1; thereafter, parents/legal guardians will report symptoms based on memory aid and medical interview by study staff. For those with multiple solicited events, the ordinal response table will be based upon the most severe solicited event.

Solicited events were recorded for trial Days 1-25, or until study completion or termination, as the maximum severity for each day. Target solicited events include irritability, vomiting, diarrhea, allergic reaction, stomatitis, and candidiasis.

The proportion of subjects in each treatment group experiencing each solicited event with mild or greater severity will be tabulated by day and overall (Table 49 and Table 50). The proportion of subjects in each treatment group experiencing each solicited event will also be tabulated by day and severity level (Table 51 and Table 52). Finally, solicited events will be analyzed by taking the most severe response over the follow-up period, dichotomizing into a binary variable (none or mild versus moderate or severe) (Table 53). Proportions for these derived binary variables will be reported along with 95% exact confidence intervals. Comparisons of proportions by treatment groups will be given as odds ratios (with 95% exact confidence intervals) and p-values from Fisher's Exact Tests.

The maximum severity occurrence of each solicited event and cough (proportion of subjects for each severity level) will be plotted for each solicited adverse event (Figure 24). Solicited events by subject will also be presented (Listing 8).

9.3.2. Unsolicited Adverse Events

As the safety profile of amoxicillin, amoxicillin-clavulanate, and cefdinir are well established, and this trial is not powered to detect new, unknown safety signals, **there will be no unsolicited event collection during this study and only protocol-defined SAE's will be collected.**

9.4. Deaths, Serious Adverse Events and other Significant Adverse Events

Detailed narratives will be given for any deaths or other protocol-defined SAEs that occurred during the study. Listings of SAEs will be presented including subject ID, AE description, AE onset date/end date, reason reported as an SAE, relationship to treatment, alternate etiology if not related, outcome, and duration of event (days) (Listing 9). SAEs will also be listed in Table 54.

9.5. Vital Signs and Physical Evaluations

Vital signs will be taken at the enrollment visit, Outcome Assessment Visit #1, and Outcome Assessment Visit #2. For each visit, by treatment group, the mean, median, standard deviation, min, and max of vital sign will be calculated for temperature, respiration rate, and pulse (Table 55). Individual vital signs measurements will be listed (Listing 10).

9.6. Concomitant Medications

Concomitant medications will be coded to the Anatomical Therapeutic Classification using the WHO Drug Dictionary. The use of prior and concomitant medications taken during the study

will be recorded on the CRFs. A by-subject listing of concomitant medication use will be presented. The use of concomitant medications during the study will be summarized by ATC1, ATC2 code and treatment group for the Safety population ([Table 56](#)).

9.7. Other Safety Measures

The number and percent of subjects visiting an emergency department, primary care provider, study physician, urgent care, or having some other type of medically attended visit due to worsening study pneumonia will be presented together with whether the subject received antibiotic, surgical treatment, or was hospitalized due to pneumonia or a complication of pneumonia ([Table 57](#)). Medically attended visits will also be listed ([Listing 13](#) and [Listing 14](#)). Presence of fever will be listed by visit ([Listing 17](#) and [Listing 18](#)).

10. OTHER ANALYSES

No other analyses are planned.

11. REPORTING CONVENTIONS

P-values ≥ 0.001 and ≤ 0.999 will be reported to 3 decimal places; p-values less than 0.001 will be reported as “<0.001”; p-values greater than 0.999 will be reported as “> 0.999”. The mean, standard deviation, and any other statistics other than quantiles, will be reported to one decimal place greater than the original data. Quantiles, such as median, or minimum and maximum will use the same number of decimal places as the original data. Proportions will be presented as two decimal places; values <0.01 will be presented as “<0.01”. Percentages will be reported to the nearest whole number; values < 1% will be presented as “<1”. Estimated parameters, not on the same scale as raw observations (e.g., regression coefficients) will be reported to 3 significant figures.

12. TECHNICAL DETAILS

SAS version 9.3 or above or R version 3.2 or above will be used to perform analyses and to generate all tables, figures and listings.

13. SUMMARY OF CHANGES IN THE CONDUCT OF THE STUDY OR PLANNED ANALYSES

Changes in the Conduct of the Study

Enrollment into the study was initiated under protocol version 2.0. Substantive changes to the protocol after study initiation are provided below.

Substantive changes in protocol version 3.0

- Removed 200mg/5mL amoxicillin and 200mg/5mL amoxicillin-clavulanate as possible dose strengths under Protocol Section 6.1.2. No subjects were prescribed under this dose.
- Clarified timing of interim analysis to be after at least 30% of the targeted subjects have completed the study instead of approximately 30%.

Changes to the Planned Analyses

There are no changes to the planned analyses as described in the protocol.

15. LISTING OF TABLES, FIGURES, AND LISTINGS

Table, figure, and listing shells are presented in Appendices 1, 2, and 3.

APPENDICES

10.2 Protocol Deviations

Table 2: Distribution of Protocol Deviations by Category, Type and Treatment Group

Category	Deviation Type	Standard Course (N=X)		Short Course (N=X)		All Subjects (N=X)	
		No. of Subj.	No. of Dev.	No. of Subj.	No. of Dev.	No. of Subj.	No. of Dev.
Eligibility/enrollment	Any type						
	Did not meet inclusion criterion	x	x	x	x	x	x
	Met exclusion criterion						
	ICF not signed prior to study procedures						
Treatment administration schedule	Other						
	Any type						
	Out of window visit						
	Missed visit/visit not conducted						
	Missed treatment administration						
	Delayed treatment administration						
Follow-up visit schedule	Other						
	Any type						
	Out of window visit						
	Missed visit/visit not conducted						
Protocol procedure/assessment	Other						
	Any type						
	Incorrect version of ICF signed						
	Other specimen not collected						
	Specimen result not obtained						
	Required procedure not conducted						
	Required procedure done incorrectly						
	Study product temperature excursion						
Treatment administration	Specimen temperature excursion						
	Other						
	Any type						
	Required procedure done incorrectly						
Treatment administration	Study product temperature excursion						
	Other						

